5.4 APPENDIX 4 DATA HANDLING CONVENTIONS

Demographic formulas

Age of onset of asthma is calculated as following:

$$\text{Age of onset of asthma} = \text{year of asthma onset} - \text{year of birth}$$

BMI is calculated as following:

$$\text{BMI} = \text{Weight in kg} / (\text{height}^2 \text{ in meters})$$

Renal function formulas

Creatinine clearance (CLcr) value will be derived using the equation of glomerular filtration rate (GFR) Bedside Schwartz

$$\text{GFR (mL/min/1.73 m}^2\text{)} = k \times \text{height (cm)} / \text{sCr (standardized serum creatinine, mg/dL)},$$

where the coefficient k=0.55 for participants ≥ 6 and < 12 years old, 0.65 for adolescent (≥ 12 years old) male participants, or k=0.55 for adolescent (≥ 12 years old) female participants.

Calculation of ACQ-IA scores

The global ACQ-7-IA score is the mean of the 7 questions of the Asthma Control Questionnaire-Interviewer Administered, 7-question version (ACQ-7-IA), and global ACQ-5-IA is the mean of the first 5 items.

For ACQ-7-IA, if more than one of the questions have missing value, the global score is invalid and will be considered as missing. If only one question has missing score, it will be imputed (pro-rated) using the completed questionnaires from the previous visit. For instance, answer to question 5 is missing at Visit 2, and all questions are completed at Visit 1. Then the question 5 score at Visit 2 is imputed as: (sum of score at Visit 2/sum of scores excluding question 5 at Visit 1) \times score of question 5 at Visit 1. If the questionnaire from the previous visit is not

complete either, the missing value will be imputed as the average of the completed questions within the current visit. Missing values of questions for ACQ-5-IA will be handled in the same way as for ACQ-7-IA score.

Analysis windows for time points

For the safety assessment, the reference date for the derivation of relative days of events or findings will be the date of first IMP dose injection. Selected safety variables will be summarized by the analysis window as defined in [Table 6](#) for the by-visit descriptive analysis. For all laboratory/vital sign/ECG variables, the summary statistics over visits for either measurements or mean change from baseline, and the plot of mean change from baseline over visits should use the centralized data only (if applicable), and should include the measurements obtained at either scheduled or unscheduled visits. All available safety measurements (from either scheduled or unscheduled visit) will be assigned to the appropriate visit window. In the event of multiple measurements of the same test in the same window, the one closest to the targeted visit date will be used for the by-visit summary. If they are at the same distance to the target day, the latest one will be used.

Table 6 - Time window for safety variables

| Visit | Target day | Time windows for | | | |
|------------------------|------------|-----------------------------------------|-----|----------------|-----------------------------------|
| | | Vital Signs, Urine Pregnancy Test | ECG | Urine Analysis | Hematology, Serum Chemistry |
| Visit 0 (Week -4±1) | -28±7 | < -14 | 1- | 1- | < -14 |
| Visit 1 (Week 0) | 1 | -14 - 1- | | | -14 - 1- |
| Visit 2 (Week 2) | 15 | 1+ - 21 | | | |
| Visit 3 (Week 4) | 29 | 22 - 42 | | | 1+ - 56 |
| Visit 4 (Week 8) | 57 | 43 - 70 | | | |
| Visit 5 (Week 12) | 85 | 71 - 98 | | 1+ - 126 | 57 - 126 |
| Visit 6 (Week 16) | 113 | 99 - 126 | | | |

| Visit | Target day | Time windows for | | | |
|----------------------------|------------|-----------------------------------------|----------------------|----------------|-----------------------------------|
| | | Vital Signs, Urine Pregnancy Test | ECG | Urine Analysis | Hematology, Serum Chemistry |
| Visit 7 (Week 20) | 141 | 127 – 154 | | | |
| Visit 8 (Week 24) | 169 | 155 – 210 | | 127 – 266 | 127 – 210 |
| Visit 9 (Week 36) | 253 | 211 – 308 | | | 211 – 308 |
| Visit 10 (Week 52, EOT) | 365 | 309 – 406 | 1 ⁺ - 406 | 267 – 406 | 309 – 406 |
| Visit 11 (Week 64, EOS) | 449 | > 406 | > 406 | > 406 | > 406 |

Note: 1:: Up to 1st IMP dose date/time; 1⁺: after 1st IMP dose date/time.

For the efficacy assessment, the reference date for the derivation of relative days of events or findings will be the day of the first IMP injection. And for the endpoints not measured daily, all available values of scheduled measurements will be assigned to the appropriate visit window according to [Table 7](#). In the event of multiple measurements of the same test in the same window, the one closest to the targeted visit date will be used for the by-visit summary. If they are at the same distance to the target day, the latest one will be used.

Table 7 - Time window for efficacy variables

| Visit | Target day | Time windows for | |
|------------------------|------------|---------------------|---------------------|
| | | Spirometry | ACQ-IA |
| Visit 0 (Week -4±1) | -28±7 | < -14 | < -14 |
| Visit 1 (Week 0) | 1 | -14 - 1- | -14 - 1- |
| Visit 2 (Week 2) | 15 | 1 ⁺ - 21 | 1 ⁺ - 21 |
| Visit 3 (Week 4) | 29 | 22 - 42 | 22 - 42 |
| Visit 4 (Week 8) | 57 | 43 - 70 | 43 - 70 |

| Visit | Target day | Time windows for | |
|----------------------------|------------|------------------|-----------|
| | | Spirometry | ACQ-IA |
| Visit 5 (Week 12) | 85 | 71 - 126 | 71 - 126 |
| Visit 6 (Week 6) | 113 | | |
| Visit 7 (Week 20) | 141 | | |
| Visit 8 (Week 24) | 169 | 127 - 266 | 127 - 210 |
| Visit 9 (Week 36) | 253 | | 210 - 308 |
| Visit 10 (Week 52, EOT) | 365 | 267 - 406 | 309 - 406 |
| Visit 11 (Week 64, EOS) | 449 | > 406 | > 406 |

Note: 1: Up to 1st IMP dose date/time; 1+: after 1st IMP dose date/time.

For the pharmacokinetics/pharmacodynamics variables summary, the reference date for the derivation of relative days of measurements will be the date of first IMP dose injection. Pharmacodynamics variables will be summarized by the analysis window as defined in [Table 8](#) by visit descriptive analyses. All available values of scheduled measurements will be assigned to the appropriate visit window. In the event of multiple measurements of the same test in the same window, the one closest to the targeted visit date will be used for the by-visit summary. If they are at the same distance to the target day, the latest one will be used.

Table 8 - Time window for pharmacokinetics and pharmacodynamics variables

| Visit | Target day | PK, ADA | Time windows for | |
|------------------------|------------|---------|-------------------------------------|----------|
| | | | Serum total IgE and Ag-specific IgE | FeNO |
| Visit 0 (Week -4±1) | -28±7 | | | < -14 |
| Visit 1 (Week 0) | 1 | 1- | 1- | -14 - 1- |
| Visit 2 (Week 2) | 15 | | | 1+ - 21 |
| Visit 3 (Week 4) | 29 | | | 22 - 42 |

| Visit | Target day | PK, ADA | Time windows for | |
|----------------------------|------------|----------------------|-------------------------------------|-----------|
| | | | Serum total IgE and Ag-specific IgE | FeNO |
| Visit 4 (Week 8) | 57 | | | 43 - 70 |
| Visit 5 (Week 12) | 85 | 1 ⁺ - 126 | | 71 - 126 |
| Visit 6 (Week 6) | 113 | | | |
| Visit 7 (Week 20) | 141 | | | |
| Visit 8 (Week 24) | 169 | 127 - 266 | 1 ⁺ - 266 | 127 - 266 |
| Visit 9 (Week 36) | 253 | | | |
| Visit 10 (Week 52, EOT) | 365 | 267 - 406 | 267 - 406 | 267 - 406 |
| Visit 11 (Week 64, EOS) | 449 | > 406 | > 406 | > 406 |

Note: 1⁺: Up to 1st IMP dose date/time; 1⁺: after 1st IMP dose date/time.

Unscheduled visits

Unscheduled visit measurements of laboratory data, vital signs, and ECG will be included in the by-visit summaries and figures, as well as the computation of baseline, worst values, and PCSAs.

5.5 APPENDIX 5 LOW, MEDIUM, AND HIGH DAILY DOSES OF INHALED CORTICOSTEROIDS (CHILDREN 6-11 YEARS) - ESTIMATED CLINICAL COMPARABILITY

| Inhaled Corticosteroid | Total Daily Dose (mcg) | | |
|--------------------------------|------------------------|--------|-------|
| | Low | Medium | High |
| Fluticasone propionate | -100 | -200 | -400 |
| Beclomethasone dipropionate | -100 | -200 | -400 |
| Ciclesonide | -100 | -200 | -400 |
| Budesonide | -200 | -400 | -800 |
| Budesonide inhalation solution | -250 | -500 | -1000 |

Source: Adapted from Japanese Guidelines for Childhood Asthma 2020.

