17.7.2.8.2 Secondary endpoints

The secondary efficacy endpoints of this study are:

- Annualized rate of severe asthma exacerbation events, during the treatment period.
- Change from baseline in pre-bronchodilator % predicted FEV1 at Weeks 2, 4, 8, 24, 52, and 64.
- Change from baseline in other lung function measurements (absolute FEV1, FVC, FEF 25-75%) at Weeks 2, 4, 8, 12, 24, 52, and 64.
- Change from baseline at Week 2, 4, 8, 12, 24, 36, 52, and 64 in ACQ-IA.

See [Section 9.2.1.1](#) on assessment of severe asthma exacerbation.

17.7.2.8.2.1 Assessment of lung function by spirometry

Lung function parameters will be assessed by centralized spirometry at screening visit (Visit 0), Visit 1 (Week 0), Visit 2 (Week 2), Visit 3 (Week 4), Visit 4 (Week 8), Visit 5 (Week 12), Visit 8 (Week 24), EOT (Week 52), and EOS visits (Week 64).

A spirometer that meets the 2005 American Thoracic Society (ATS)/European Respiratory Society (ERS) recommendations will be used. Spirometry should be performed in accordance with the ATS/ERS guidelines ([8](#)). For prebronchodilator measured parameters, including FEV1, peak expiratory flow (PEF), FVC, and FEF 25% to 75%, spirometry will be performed after a wash out period of bronchodilators according to their action duration, for example withholding the

last dose of salbutamol/albuterol for at least 6 hours, withholding the last dose of LABA for at least 12 hours (ultra-LABA like vilanterol should be withheld for at least 24 hours), and withholding the last dose of LAMA for at least 24 hours.

At all related visits, spirometry will be performed either in the AM or PM, but preferably in the AM, and at approximately the same time at each visit throughout the study. The same spirometer and standard spirometric techniques, including calibration, will be used to perform spirometry at all visits and whenever possible, the same person should perform the measurements.

Pulmonary function tests will be measured in the sitting position; however, if necessary to undertake the testing with the patient standing or in another position, this should be noted on the spirometry report. For any patient, the position should be consistent throughout the study.

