Patients and/or parent(s)/caregiver(s)/legal guardian(s) are asked to recall how their asthma and/or their child's asthma, respectively, has been during the previous week and to respond to the symptom and bronchodilator use questions on a 7-point scale (0 = no impairment, 6 = maximum impairment). Clinic staff scores the % predicted FEV1 on a 7-point scale based on the pre-central reading spirometry result displayed immediately after the spirometry testing. Then, the questions are equally weighted and the global ACQ-7 score is the mean of the 7 questions and therefore between 0 (totally controlled) and 6 (severely uncontrolled) (see [Section 17.7.2.15](#)).

Higher score indicates lower asthma control. Patients with a score below 1.0 reflect adequately controlled asthma and patients with scores above 1.0 reflect inadequately controlled asthma. On the 7-point scale of the ACQ-7, a change or difference in score of 0.5 is the smallest change that can be considered clinically important, corresponding to the MCID defined by the developer.

For statistical analysis, ACQ-7 global score is calculated by the sponsor using the BMS post central reading value of the %predicted FEV1 for the question 7 of the questionnaire.

Measurement properties such as reliability and ability to detect change have been documented in the literature ([10](#)).

ACQ-5-IA (Asthma Control Questionnaire–Interviewer Administered, 5-question version)

The ACQ-5-IA will be deduced from the responses to the first 5 questions of ACQ-7-IA and will be used for children ≥ 6 years to <12 years old at screening and baseline for eligibility evaluation.

Higher score indicates lower asthma control. Patients with a score below 1.0 reflect adequately controlled asthma and patients with scores above 1.0 reflect inadequately controlled asthma. On the 7-point scale of the ACQ-5, a change or difference in score of 0.5 is the smallest change that can be considered clinically important, corresponding to the MCID defined by the developer.

Measurement properties such as reliability and ability to detect change have been documented in the literature.

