- Measure vital signs (blood pressure, heart rate, respiratory rate, body temperature, and weight).
- Call IVRS/IWRS to register visit and obtain treatment kits number.
Record all concomitant medication use (including but not limited to asthma background controller, reliever, and vaccine); inquire about AEs/SAEs.
- Administer ACQ-7.
- Assess menstruation status.
- Obtain blood samples for:
 - Hematology (see [Section 17.7.2.8.3.5](#) for details),
 - Serum chemistry (see [Section 17.7.2.8.3.5](#) for details).
- Obtain urine pregnancy test (dipstick) if female patients are of childbearing potential (who have commenced menstruating).
- Dispense and administer IMP:
 - Patients will be monitored at the study site for a minimum of 30 minutes after the injection if patients receive IMP on site.
 - The injection training is for parent(s)/caregiver(s)/legal guardian(s) who are willing to perform injection administration at home (see [Section 17.7.2.7.1.3](#) for details). If parent(s)/caregiver(s)/legal guardian(s) have been trained by the Investigator or designee to administer IMP by demonstration at not less than 3 visits, under the close supervision of the Investigator or delegate, parent(s)/caregiver(s)/legal guardian(s) will

perform the injection, including feedback on technique by the Investigator or delegate. The training should be documented in the patient's medical records.

- Record observation of a minimum of 30 minutes after the injection monitored by IMP giver if patients receive IMP at home.
- Remind patients and their parent(s)/caregiver(s)/legal guardian(s) to use salbutamol/albuterol as reliever medication as instructed by Investigator.
- Remind patient and their parent(s)/caregiver(s)/legal guardian(s) to continue their stable dose of ICS alone or in combination with a second controller.
- Schedule a site visit 16 weeks later (Week 52 \pm 3 days) at approximately the same time of this visit.

17.7.2.9.1.4.10 Telephone contact at Weeks 40, 44, and 48 (\pm 3 days)

See [Section 10.1.2.10](#).

17.7.2.9.1.4.11 Visit 10 (Week 52 [\pm 3 days]), End-of-treatment visit

- Measure vital signs (blood pressure, heart rate, respiratory rate, body temperature, weight, height).

- Call IVRS/IWRS to register EOT visit.

- Record all concomitant medication use (including but not limited to asthma background controller, reliever, and vaccine); inquire about AEs/SAEs.

- Administer ACQ-7.

- Measure FeNO:

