1.2 OBJECTIVES AND ENDPOINTS

Objectives

The primary objective of this substudy is to evaluate the efficacy of dupilumab in children from Japan who are 6 to <12 years of age with uncontrolled, persistent asthma.

The secondary objectives of this substudy are:

- To evaluate the safety and tolerability of dupilumab in Japanese pediatric patients with asthma.
- To evaluate dupilumab in Japanese pediatric patients with asthma with regard to:
 - Systemic exposure,
 - anti-drug antibodies (ADAs),
 - Biomarkers.

Endpoints

The primary endpoint of this substudy is change from baseline in pre-bronchodilator % predicted FEV1 at Week 12.

The secondary endpoints of this substudy include:

- Annualized rate of severe asthma exacerbation events, during the treatment period.
- Change from baseline in pre-bronchodilator % predicted FEV1 at Weeks 2, 4, 8, 24, 52, and 64.

- Change from baseline in other lung function measurements (absolute FEV1, FVC, FEF 25-75%) at Weeks 2, 4, 8, 12, 24, 52, and 64.
- Change from baseline at Week 2, 4, 8, 12, 24, 36, 52, and 64 in ACQ-IA.
- The number (n) and percentage (%) of patients experiencing any treatment-emergent adverse event.
- Serum dupilumab concentrations.
- ADAs.
- Serum: Total immunoglobulin (IgE).
- Fractional exhaled nitric oxide (FeNO).

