For change from baseline in pre-bronchodilator % predicted FEV1, absolute FEV1, FVC, and FEF 25%-75%, IE handling strategies are similar to the primary endpoint. Descriptive statistics (number of participants, mean, SD, median, minimum and maximum) and the 95% CI (based on t-distribution) of the mean will be presented over visits (Weeks 2, 4, 8, 24, 52, 64 for % predicted FEV1, and Weeks 2, 4, 8, 12, 24, 52, 64 for the others). In addition, figure of mean change from baseline (with corresponding standard error) will be presented for the parameter over visits.

Change from baseline in ACQ-IA

The global ACQ-7-IA score is the mean of the 7 questions of the Asthma Control Questionnaire—Interviewer Administered, 7-question version (ACQ-IA-7), and global ACQ-5-IA is the mean of the first 5 items.

For change from baseline in global ACQ-5-IA and ACQ-7-IA scores, IE handling strategies are similar to the primary endpoint. The methods for handling missing values of the questions are described in [Section 5.4](#). No missing data imputation will be performed for the global scores. Descriptive statistics (number of participants, mean, SD, median, minimum and maximum) and the 95% CI (based on t-distribution) of the mean will be presented over visits. Figure of mean change from baseline (with corresponding standard error) will be presented over visits.

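### Japan substudy: ACQ-7-IA is analysed at Week 36, where no spirometry is scheduled, so its FEV1 item is filled by a ratio rule that can be undefined or leave the 0–6 scale

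*SAP*

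**What the plan says.** Week 36 is a planned ACQ time point. Section 1.2 of the Japan SAP lists among the secondary endpoints "Change from baseline at Week 2, 4, 8, 12, 24, 36, 52, and 64 in ACQ-IA", and Section 3.3 plans by-visit summaries of both scores: "For change from baseline in global ACQ-5-IA and ACQ-7-IA scores, IE handling strategies are similar to the primary endpoint". In the protocol's Japan visit schedule (17.7.2.9.1), the Visit 9 (Week 36) list includes "Administer ACQ-7" but no spirometry.

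The Japan spirometry section (17.7.2.8.2.1) goes straight from Week 24 to Week 52: "Visit 4 (Week 8), Visit 5 (Week 12), Visit 8 (Week 24), EOT (Week 52), and EOS visits (Week 64". Table 7 of the Japan SAP agrees. At Visit 9 it gives ACQ-IA a window of days 210–308 and leaves the spirometry cell empty. Height is also not taken at Visit 9 (17.7.2.8.3.2).

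Item 7 depends on spirometry. For analysis, "ACQ-7 global score is calculated by the sponsor using the BMS post central reading value of the %predicted FEV1 for the question 7".

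Appendix 4 (Section 5.4) of the Japan SAP sets the missing-item rules:
- More than one item missing: the global score is missing.
- One item missing: "If only one question has missing score, it will be imputed (pro-rated) using the completed questionnaires from the previous visit". The worked example multiplies the item's earlier score by the ratio "sum of score at Visit 2/sum of scores excluding question 5 at Visit 1".
- One item missing and the earlier questionnaire also incomplete: the mean of the items answered at the current visit.

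Nothing exempts item 7 or Week 36, deals with a zero denominator, or limits the result to the item's range.

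**The concern.** A rule for one missing item is normally a provision for occasional gaps. Here the schedule creates the gap at one visit, so the rule becomes the routine way of obtaining item 7 at Week 36. It sets the FEV1 item by assuming that lung function has moved in proportion to symptoms, activity limitation and reliever use since Week 24. The ACQ-7 at that visit would then be presented as a seven-item score that includes lung function, when none was measured then. The arithmetic is also unsafe, because the denominator can be zero and the result has no upper limit.

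At stake is one listed secondary efficacy summary. Thirteen children are enrolled, and results are shown by dose regimen as well as overall, with as few as three children in a regimen. One distorted value can therefore move a group mean noticeably.

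**Working it through.** The documents give no numerical figure for this rule, so there is none to reproduce. The check applies the rule as written.

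**Inputs**
- Each item is scored 0 to 6, the global score is the mean of seven items, and the smallest important change is 0.5 (protocol 17.7.2.8.2.2).
- S = sum of items 1–6 at Week 24 and C = sum of items 1–6 at Week 36, each between 0 and 36.
- Q = item 7 at Week 24, the previous visit with both ACQ and spirometry.
- 13 children enrolled, with at least 3 in each regimen (Japan SAP 1.1).

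**Formula.** With items 1–6 answered at Week 36 and a complete Week 24 questionnaire:

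imputed item 7 = (C / S) × Q

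ACQ-7 at Week 36 = [C + (C / S) × Q] / 7 = (C / S) × (S + Q) / 7 = (C / S) × ACQ-7 at Week 24

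So the Week 36 score is the Week 24 score rescaled by the change in the other six items.

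**Undefined case.** If S = 0, the rule divides by zero. The within-visit fallback does not apply, because the Week 24 questionnaire is complete.

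**Off-scale case.** The imputed item exceeds 6 whenever C / S > 6 / Q, that is, above 2 for Q = 3, above 1.5 for Q = 4 and above 1 for Q = 6.

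**Illustrations.** The item 7 unchanged column is a reference point, not a proposed method.

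| S | C | Q | Imputed item 7 | ACQ-7 by rule | Item 7 unchanged | Highest valid score (item 7 = 6) |
|---|---|---|---|---|---|---|
| 2 | 6 | 3 | 6/2 × 3 = 9 | 15/7 = 2.14 | 9/7 = 1.29 | 12/7 = 1.71 |
| 6 | 2 | 3 | 2/6 × 3 = 1 | 3/7 = 0.43 | 5/7 = 0.71 | 8/7 = 1.14 |
| 2 | 10 | 3 | 10/2 × 3 = 15 | 25/7 = 3.57 | 13/7 = 1.86 | 16/7 = 2.29 |

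In the first row the rule exceeds the unchanged-item score by 6/7 = 0.86, more than the 0.5 important change. In the second row the gap is 2/7 = 0.29, below it. Baseline is common to both calculations, so the same gaps pass into change from baseline.

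**Effect on a mean.** One child like the first row moves a three-child regimen mean by 0.86 / 3 = 0.29 and a 13-child mean by 0.86 / 13 = 0.07. One child like the third row (gap 12/7 = 1.71) moves them by 0.57 and 0.13.

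**Range of inputs.** There are 37 × 37 × 7 = 9,583 combinations of S, C and Q. Of these, 37 × 7 = 259 are undefined and 2,178 give an item above 6. These are counts of possible inputs, not probabilities.

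**The case against.** The case for leaving this alone is that little depends on it. It concerns one of two ACQ scores at one of eight post-baseline time points in a descriptive substudy. ACQ-5-IA at Week 36 does not use item 7, and the primary endpoint is FEV1 at Week 12. The SAP plans no responder analysis on the 0.5 threshold. In the illustrations, the rule and the unchanged item put the Week 36 score on the same side of the protocol's 1.0 control value. All of this stands and limits the weight of the point. It does not make the stated rule give a usable Week 36 ACQ-7.

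Three stronger readings are tempting, and the documents do not support them.
- A reader might infer that all 13 children receive a ratio-imputed score. Thirteen is an upper bound. The documents do not say how many reach Week 36 or complete the Week 24 questionnaire. An incomplete Week 24 questionnaire leads to the within-visit mean, and a second missing Week 36 item makes the score missing. An early end-of-treatment visit includes spirometry and could fall in the window, as could an unplanned test.
- A reader might infer that the score contains no FEV1 at all. It contains the Week 24 FEV1 item, rescaled. What it lacks is any Week 36 measurement.
- A reader might infer that undefined or off-scale values will be common. S = 0 needs no symptoms, limitation or reliever use at Week 24 in children who entered with an ACQ-5 of at least 1.5. That is possible, but its frequency is not given.

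It can also be said that the root cause is the protocol's visit schedule, not the scoring rule. That is correct, but the SAP decides what is reported and can be corrected cheaply.

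**Conclusion.** The point holds in this form. By schedule, item 7 is missing at Week 36 for up to 13 children. Where items 1–6 are answered and the Week 24 questionnaire is complete, the plan turns the Week 36 ACQ-7 into the Week 24 ACQ-7 times C / S. That value contains no Week 36 lung function, is undefined at S = 0, and can exceed what any valid item 7 would allow (2.14 against 1.71 in the first illustration).

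The absence of item 7 and the algebra rest only on the schedule and the stated rule. The size of the distortion rests on illustrative item sums, and its frequency cannot be derived from the documents. The zero-denominator and no-cap defects apply at any visit with a single missing item, but only Week 36 is affected systematically. The correction is worth making and modest in weight. No conclusion on the primary endpoint depends on it.

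**What to change.** In the Japan SAP:
- **Week 36:** report ACQ-5-IA only and drop ACQ-7-IA at that time point. Record this in Section 3.8 as a change to the protocol-planned analyses, since the protocol's flow chart gives ACQ-7 the follow-up role and ACQ-5 the eligibility role.
- **Other visits, one of items 1–6 missing:** use the mean of the items answered at the same visit. This is already the SAP's fallback, is always defined and stays within 0–6.
- **Other visits, item 7 missing:** set ACQ-7-IA to missing. Do not fill the FEV1 item from the symptom and reliever items, whether by the ratio or by the within-visit mean.

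The cost is a revised scoring paragraph and an entry in Section 3.8. The Week 36 ACQ-7 summary is lost, though it would have held no Week 36 FEV1, and so are occasional ACQ-7 scores at visits where spirometry was missed. Settle the derivation before the core database lock, which Section 3.7 makes the basis of the final analyses.
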